TeleMonitoring to Improve Substance Use Disorder Treatment After Detoxification

NCT02269787

10/01/2014

Protocol (10/1/2014)

Sample and procedures

Patients entering one of two psychiatry units within the same health care system were included on the basis of (1) undergoing detoxification for alcohol and/or opioid dependence; and having (2) sufficient cognitive functioning to understand study procedures (i.e., able to answer the Montreal Cognitive Assessment's section on Orientation; Nasreddine et al., 2005), (3) access to a cell or land line telephone when not hospitalized, and (4) at least one person who would know of their whereabouts after discharge, for whom contact information was available. After receiving an introduction to the study, participants signed an informed consent form. All study procedures were approved by the VA Central Institutional Review Board. Patients who provided informed consent completed the baseline interview. After the baseline interview, participants were randomly assigned to condition (ETM or UC) using random numbers generated by a computer program.

Regarding follow-ups, the research assistant, blinded to patients' condition assignment, collected self-report data from patients by telephone at three months post-baseline (which was upon completion of the intervention for patients in the ETM condition) and at three months after the three-month follow-up (i.e., six months post-baseline). We used an intent-to-treat design and so followed all participants irrespective of participation in the intervention. Follow-up assessments were conducted by telephone because not all patients resided in close geographical proximity to the inpatient facility.

Conditions

Usual Care. All patients, regardless of condition, received usual inpatient detoxification which consisted of medically supervised withdrawal. The health care system had available post-detoxification addiction outpatient and residential specialty care and pharmacotherapy. Study participants, as part of usual care, were offered by detoxification staff a referral to or an appointment with addiction treatment services, if they chose to consider seeking treatment.

ETM. Patients assigned to the ETM condition received usual care plus the ETM intervention. ETM consisted of one 50-minute individual session during the inpatient stay and 12 weekly 15-minute telephone sessions from the same TeleCoach who conducted the in-person session.

The in-person session enhanced procedures in McKay, Van Horn, & Morrison's (2010a) manual for implementing telephone monitoring with addiction patients transitioning from more to less intensive treatment. It provided an orientation to the telephone monitoring protocol, which was enhanced by Motivational Interviewing and Contracting. Motivational components included the TeleCoach's empathy, conveying the patient's responsibility for change, and supporting the patient's self-efficacy to make changes, while addressing post-detoxification engagement in addiction treatment and mutual-help. Participants completed a contract containing two main elements: information that attending treatment and mutual-help increases the chances of remaining abstinent; and an intention to attend addiction treatment and/or mutual-help, with as much specificity as the patient could provide regarding these plans. Participants were informed of ETM's reinforcers for beginning and participating in treatment and mutual-help, and given *The Next Step Toward a Better Life* (SAMHSA, 2014), which tells people completing detoxification what to expect physically and psychologically post-discharge, encourages use of treatment and mutual-help, and provides tools for remaining clean and sober.

Telephone sessions also enhanced procedures in the McKay et al. (2010a) protocol. Patients were expected to complete one 15-minute telephone call per week for 12 weeks. When the patient failed to answer a call, the TeleCoach made at least two more attempts at that scheduled contact, and when successful, the initial non-response was discussed. Patients received reinforcements for completing 6 and then 12 phone calls (e.g., tote bags, key chains). During each telephone session, patients completed the Risk Assessment Worksheet (McKellar et al., 2012) about substance use and compliance with treatment and mutual-help since the last call. Telephone sessions were enhanced with prompts and reinforcements. The TeleCoach

checked whether participants had attended planned treatment sessions and mutual-help meetings, and reminded them to return even if they had missed a session or meeting. Participants received social reinforcements for attending treatment and mutual-help, i.e., a personal congratulations letter from the TeleCoach for entering treatment and attending the first post-detoxification mutual-help meeting, certificates for abstinence milestones (2, 4, and 8 weeks), and a certificate plus medallion for abstinence through 12 weeks.

2.3 Measures

At baseline, patients were asked whether they had received previous inpatient detoxification (no or yes). At follow-ups, patients were asked whether they had received inpatient detoxification since the previous interview (in the past three months; no or yes).

At baseline, patients were asked whether they had received previous outpatient treatment for alcohol and/or drugs in their lifetime and in the past 30 days. At follow-ups, patients were asked whether they had received outpatient treatment for alcohol and/or drugs since the last interview (in the past three months; no or yes). At baseline and follow-ups, patients were asked whether they had attended a 12-step meeting in the past three months and if so, how many meetings.

At baseline and follow-ups, we used the Addiction Severity Index (ASI; McLellan, Cacciola, Alterman, Rikoon, & Carise, 2006) to assess alcohol use, drug use, and psychiatric severity. In each area, items measured the number, extent, and duration of symptoms in the past 30 days. ASI composite scores were produced from sets of items that were standardized and summed to provide internally consistent evaluations of patient status in the problem areas (McLellan et al., 2006). They range from 0 to 1, with higher scores indicating poorer outcomes. In addition, to ensure the clinical utility of findings, we report responses to the ASI items referring to the past 30 days that assessed number of days drank alcohol (0-30), number of days used opioids (0-30), experienced serious thoughts of suicide (that is, seriously considered a plan for taking own life) (no or yes), and attempted suicide (no or yes).

We also used the Brief Addiction Monitor (which is required in VA for measurement based substance use disorder care) at baseline and follow-ups (Cacciola et al., 2013; CESATE, 2010), which yields two composite scores referring to the past 30 days. (1) *Substance use* is the sum of three items, i.e., number of days drank alcohol; had at least 5 drinks (if a man) or at least 4 drinks (if a woman); and used any illegal/street drugs or abused any prescription medications (for each, 0=0, to 4=16-30 days). (2) *Risk factors* for substance use is the sum of five items, e.g., physical health (0=excellent, 4=poor); number of nights having trouble falling or staying asleep (0=0, 4=16-30 days); in any situations or with any people that might increase risk for using alcohol or drugs (0=0, 4=16-30 days).

At baseline and follow-ups self-efficacy was assessed with the Brief Situational Confidence Questionnaire (Breslin, Sobell, Sobell, & Agrawal, 2000). Eight items asked patients to rate their level of confidence in resisting drinking and using drugs as a response to different types of situations (e.g., unpleasant emotions, social pressure to drink/use), and then responses were averaged such that higher scores indicate more self-efficacy (Cronbach's alpha = .91, .92, and .91 at baseline and 3 and 6 months, respectively).

2.4 Analysis Plan

We first compared patients randomly assigned to ETM or UC on baseline demographic and outcome characteristics. We then used analysis of covariance (ANCOVAs) to compare the ETM and UC groups on outcomes at the 3- and 6-month follow-ups. Covariates were the baseline value of the outcome and the inpatient detoxification unit.

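### Intent-to-treat is declared, but the plan does not say how patients who miss the 3- or 6-month interview enter the ANCOVAs; outcome-related non-response that differs by arm could bias them either way

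*Combined protocol and SAP*

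**What the plan says.** Section 2.4 is the whole analysis plan. After a baseline comparison of the randomised groups it states: "We then used analysis of covariance (ANCOVAs) to compare the ETM and UC groups on outcomes at the 3- and 6-month follow-ups". The adjustment is: "Covariates were the baseline value of the outcome and the inpatient detoxification unit".

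Under Sample and procedures the design is described this way: "We used an intent-to-treat design and so followed all participants irrespective of participation in the intervention". The same section says that a blinded research assistant "collected self-report data from patients by telephone at three months post-baseline (which was upon completion of the intervention for patients in the ETM condition"), and again at six months. It gives the reason for the route: "Follow-up assessments were conducted by telephone because not all patients resided in close geographical proximity to the inpatient facility".

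No section gives a rule for a missed interview. There is no imputation, likelihood-based repeated-measures model, comparison of those lost with those kept, or sensitivity analysis. No follow-up rate, sample size or SD is stated.

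**The concern.** The intent-to-treat sentence settles who is pursued for follow-up and that non-adherence is no reason to stop following a patient. It does not settle what happens to a randomised patient with no 3- or 6-month outcome. With no rule, a row with a missing outcome drops out of an ANCOVA. Each comparison would then rest on patients reached at that call, and the 6-month model would make no use of a 3-month outcome already in hand.

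This trial is more exposed than most. Outcomes are self-reported by telephone, and regular telephone contact is also the intervention, described for ETM only. Coaching ends at about the time of the 3-month interview, so the issue arises there at least as much as at 6 months. If relapse affects whether a patient is reached, and does so differently in the two arms, a real ETM benefit could be understated, or a benefit could be exaggerated or created.

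**Working it through.** The plan states no figure to reproduce. Everything numerical below is an assumption, used to show direction and order of size.

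**1. When bias arises.** Let m be the fraction missing in an arm and d the adjusted mean of non-responders minus responders, in SD units, with higher scores worse. The complete-case bias in ETM minus UC is m(UC)·d(UC) − m(ETM)·d(ETM).
- d = 0.5 in both arms, 10% missing in ETM and 30% in UC: 0.30×0.5 − 0.10×0.5 = +0.10 SD.
- Rates reversed: −0.10 SD. Equal rates: 0.
- In a simulation of 1,000,000 patients with no true effect, missingness depending only on arm and baseline gave a bias of 0.001 to 0.002 SD, even with 86% against 71% reached. Unequal reach alone is therefore not enough.

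**2. Binary outcome (unadjusted).** P(using | reached) = p·r_u / [p·r_u + (1 − p)·r_n], where p is the true proportion using and r_u, r_n are the reach of users and non-users. Take p = 50% in both arms and r_n = 85%.
- UC, users reached 65%: 0.325/(0.325 + 0.425) = 43.3%.
- ETM, users reached 80%: 0.400/(0.400 + 0.425) = 48.5%.
- Spurious difference: 5.2 points against ETM. With the arms swapped it is 5.2 points in favour.
- Both arms appear better than the true 50%. ETM, the better-reached arm, looks worse only relative to UC.
- If users' reach is 5 or 10 points below 80% in one arm, the spurious difference is 1.6 or 3.3 points. Equal reach gives 0.
- With a true 10-point benefit (ETM 40% using), 65% (UC) and 80% (ETM) of users reached gives 43.3% − 0.32/0.83 = 43.3% − 38.6%, or 4.8 points before rounding. The reverse gives 48.5% − 0.26/0.77 = 48.5% − 33.8% = 14.7 points.

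**3. Scores.** Simulation with no true effect, 400,000 per arm, and correlations of 0.4 (baseline with each follow-up) and 0.6 (3 with 6 months). Average reach is 80% per arm and visit. Logistic slopes of loss on the score, UC/ETM, are 0.8/0.27 (mild), 0.8/0 (moderate) and 1.4/0 (strong). Reach at −1/+1 SD is 91/68% for slope 0.8, 84/76% for 0.27 and 96/61% for 1.4. Bias in SD:

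| Loss mechanism | Stated ANCOVA: mild, moderate, strong | Three-visit likelihood model |
|---|---|---|
| 3-month call, loss follows current score | 0.076, 0.123, 0.185 | 0.061, 0.098, 0.151 |
| 6-month call, loss follows current score | 0.077, 0.119, 0.186 | 0.062, 0.095, 0.151 |
| 6-month call, loss follows 3-month score; 3-month loss random | 0.041, 0.061, 0.097 | 0.009, 0.010, 0.019 |
| As above, but 3-month loss also follows that score | 0.040, 0.064, 0.096 | 0.016, 0.021, 0.043 |

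Swapping arms reverses the sign (moderate case at 3 months: −0.125 and −0.100). The same slope in both arms gives 0.005 or less. When loss follows current status, the model leaves about 80% of the bias (0.098/0.123 = 0.80), or 84–87% if this happens at both calls.

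**4. Why delta must vary by arm.** In the 65/80% example the odds ratio of use, unreached against reached, is (0.175/0.075)/(0.325/0.425) = 3.05 in UC and (0.100/0.075)/(0.400/0.425) = 1.42 in ETM. Applying each to its own arm returns 50% against 50%. Applying 3.05 to both leaves 3.0 points.

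**The case against.** The case against is substantial, and most of it limits the point rather than removing it.

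- A reader might infer that the plan has no analysis population or ignores intent-to-treat. It does not: intent-to-treat is declared and groups are compared as assigned. The gap is how patients without follow-up data enter.
- A reader might infer that the plan prescribes complete cases. No text says so; it is the default of an ANCOVA with no stated rule.
- A reader might infer that the coaching makes ETM patients easier to interview, so the direction is known. The provision that "When the patient failed to answer a call, the TeleCoach made at least two more attempts at that scheduled contact" concerns coaching calls. Outcome calls came from a blinded assistant, and both arms needed a telephone and a locator contact. These steps may reduce loss, but they are not an analysis method.
- Baseline-adjusted ANCOVA by visit is legitimate, and the proposed model removes little bias when loss follows current status. That stands, and is why the sensitivity analyses carry equal weight.
- The top of the score range, 0.19 SD, needs strong outcome-dependent loss in one arm and none in the other.
- The text is in the past tense and Section 2.3 already reports 3- and 6-month reliabilities, so changing the main model now may be post hoc. That stands too.

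**Conclusion.** The concern holds in this form: intent-to-treat is declared, but handling of missed interviews is unspecified, and the default analysis is open to bias in either direction. The condition is non-response that is related to the outcome after allowing for baseline value and unit, and that differs by arm in rate or mechanism. If non-response depends only on arm, baseline value and unit, there is essentially no bias.

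The omission is certain; its size is not known. On the assumed inputs it is about 2 to 5 percentage points for a binary outcome and 0.08 to 0.19 SD for a score when loss follows current status, with either sign. Without numbers reached by arm and visit, a reader cannot judge either follow-up comparison. The change should be made, with medium confidence that it would matter to the result.

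**What to change.** 1. Define the analysis set as all randomised patients by assigned arm, and report numbers reached by arm and visit.
2. For scores, use a likelihood-based longitudinal model with baseline, 3 and 6 months as outcomes: common baseline mean, arm × visit, unit × visit, unstructured covariance. For binary and count outcomes, use multiple imputation by arm from baseline, unit and the other visit, with a simpler imputation model for rare events such as suicide attempt. Keep the stated ANCOVAs as supporting, and label the change post hoc if follow-up data have been seen.
3. State that step 2 removes only bias predictable from observed data. On the assumed inputs about 80% remains when loss follows current status. When 6-month loss follows the 3-month score, 0.01–0.02 SD remains if 3-month loss is random and about 0.015–0.04 SD if it also depends on that score.
4. With equal weight, add delta-adjusted not-at-random sensitivity analyses at both visits, with delta varied separately by arm and in both directions. Counting unreached patients as using can only be an extra scenario. In the example above it gives 57.5% in both arms, but if non-users' reach were 85% in UC and 90% in ETM it would give 57.5% against 55.0%, a spurious 2.5 points for ETM.

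The cost is modest programming, wider intervals in the sensitivity analyses and a possible post hoc label. No new data are needed.
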